**11.0**                **Drug Information: Cetuximab**

The product will be provided from commercial supply.

**11.4**                    Formulation

Cetuximab is an anti-EGFR receptor humanized chimeric monoclonal antibody. Cetuximab is expressed in SP2/0 myeloma cell line, grown in large scale cell culture bioreactors, and purified to a high level purity using several purification steps

including protein A chromatography, ion exchange chromatography, low pH treatment, and nanofiltration. Cetuximab is not known to be a vesicant.

**11.5**            Supply

The product is formulated to 2 mg protein/mL with phosphate buffered saline, pH 7.2 ± 0.2 and aseptically filled into sterile glass vials, 100 mg per 50 cc vial, and stored as a liquid at 2 to 8° C. Each vial contains the following active and inactive ingredients per 1.0 ml: 2 mg of cetuximab, 145 nmol/L sodium chloride, and 10 mmol/L sodium phosphate.

**11.6**            Safety Precautions

Appropriate mask, protective clothing, eye protection, gloves and Class II vertical-laminar-airflow safety cabinets are recommended during preparation and handling.

**11.7**            Preparation and Administration:

11.7.5            Cetuximab is provided by ImClone as an injectable solution, in single-use, ready-to-use 50-mL vials containing 2 mg/mL of product. Cetuximab requires no dilution. Cetuximab should not be mixed with or diluted with other drugs or solutions for infusion such as 5%-glucose.

11.7.6            The dose and volume of the study drug to be infused are dependent upon the patient's actual BSA. The infusion rate must never exceed 10 mg/minute (5 mL/minute). The dose may subsequently be reduced for individual patients, depending on a patient's toxicity. For the duration that patients are on cetuximab therapy, adverse event monitoring should be done continuously. Patients will be evaluated for adverse events at each visit and are to be instructed to call their physician to report any adverse events between visits.

11.7.7            Cetuximab may be administered via a gravity drip, infusion pump, or syringe pump. Cetuximab administration requires an in-line low protein-binding 0.22 micron filter. Note: one filter per dose should be sufficient, but further filters can be used if a filter becomes blocked.

Administration via Infusion Pump or Gravity Drip

Calculate the appropriate volume of cetuximab based on the dose and using an appropriate sterile syringe (min 50 mL) draw up the required volume from the vial(s). Add the cetuximab into a sterile evacuated container or bag (glass administration containers are not recommended). Do not shake. Attach an infusion line with a low protein binding 0.22 micron in-line filter. Use a gravity drip or an infusion pump for administration. Set and control the rate as noted above and infuse the whole dose.

Administration via Syringe Pump

Calculate the appropriate volume of cetuximab based on the dose and using an appropriate sterile syringe (min 50 mL) draw up the required volume from the vial(s). Do not shake. Remove the needle, and put the syringe into the syringe pump. Attach tubing with a low protein-binding 0.22 micron filter. Set and control the rate as described above. Make sure that the whole dose has been infused.

Studies have been conducted to demonstrate the compatibility of cetuximab drug product with various infusion systems. Some

examples of materials, IV containers, infusion sets, and filters tested and recommended for use with cetuximab are listed below. For further examples of approved materials, please see the Investigator Brochure.

#### Recommended IV Containers

- IntraVia™ IV Bag with PVC Ports, Model No. 2J8002 (Baxter Healthcare Corporation)
- EVA™ IV Bag, Model No. 2B8152 (Baxter Healthcare Corporation)
- LifeCare™ IV Bag, Model No. 7951-12 (Abbott Laboratories)

#### Recommended Infusion Sets

- Vented Continu-Flo Solution Set™, Model No. 2C6541s (Baxter Healthcare Corporation) to be used with an in-line filter set, Model No. 2679 (Abbott Laboratories)
- Vented Paclitaxel Set™ with 0.22-µm downstream high-pressure in-line filter, Model No. 2C7553 (Baxter Healthcare Corporation)

#### Recommended Filters

- Vented Continu-Flo Solution Set™, Model No. 2C6541s (Baxter Healthcare Corporation) to be used with an in-line filter set, Model No. 2679 (Abbott Laboratories)
- Intrapur Plus (B. Braun AG) reference number 409 9800
- Poly-lined filtered Extension set (Alaris Medical Systems) reference number C20350

11.7.8 Normal saline should be used to clear the infusion set of residual cetuximab. The delivered drug product is > 95% for all recommended infusion sets when flushed with 50 mL of normal saline. Use a separate line for cetuximab infusion.

11.7.9 Storage Requirements/Stability: Cetuximab must be stored under refrigeration at +2°C to +8°C (+36°F to +46°F). DO NOT FREEZE CETUXIMAB. Drug supplies must be kept in a secure, limited access storage area under the recommended storage conditions. Once cetuximab is removed from the vial, the recommended maximum storage time in the infusion container or syringe is 8 hours at room temperature or 12 hours in the refrigerator.

## **11.8**

### Adverse Events:

- Hematologic: Leukopenia
- Gastrointestinal: Nausea, vomiting, diarrhea, anorexia, mucous membrane disorder, stomatitis, reduced kidney or liver function
- Dermatologic: Rash, acne, dry skin, pruritus
- Circulatory: Deep vein thrombosis
- Neurological: Confusion, disorientation, seizure, coma; rarely, encephalitis
- Allergy: Allergic reaction, anaphylactoid reaction
- Other: Asthenia, fever, dyspnea, headache, chills, nail disorder, myalgia, arthralgia

## 12.0 Radiation Therapy

### 12.4 General Considerations:

All the patients in this study will receive definitive radiotherapy. Definitive radiotherapy will begin one week following the administration of the loading dose of cetuximab.

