## 6.0 Schema

## 7.0 Study Design

### 7.1 Overview

Patients will receive a single dose of cetuximab 400 mg/m^2 (Day 0). On day 7 (+/- 1 day), a repeat biopsy will be performed. Within approximately 4 days, definitive radiation will begin (70 Gy in 35 fractions to the gross tumor, 50-60 Gy to subclinical target volumes) concurrent with weekly cetuximab 250 mg/m^2. Twelve to 14 weeks following the completion of cetuximab-radiation, patients will undergo standard restaging and treatment, including CT-PET, repeat laryngoscopy and tumor site biopsies. Patients with evidence of persistent tumor may undergo surgical salvage and/or neck dissection.

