### 7.2 Research Component (Treatment with cetuximab and associated biopsies)

All patients will sign an informed consent for clinical and research biopsies. All biopsies will be performed by an otolaryngologist or oral surgeon who is a co-investigator of the study. The proposed tissue accrual should be adequate for all of the proposed studies.

- 7.2.1 Research Biopsy #1: Patients will be consented and enrolled in this study prior to this biopsy. The biopsy will be performed no more than 4 weeks prior to the loading dose of cetuximab. It will be performed under local anesthesia (in the event a patient requires further clinical staging or confirmation of diagnosis under general anesthesia, the research biopsy may be performed at that time.) This pre-treatment biopsy will be performed for research purposes if a suitable clinical biopsy specimen is not available. A clinical specimen will be suitable if the biopsy was performed within 4 weeks of the loading dose of Cetuximab.
- 7.2.2 Research Biopsy #2: This will be done 7 days (+/- 1 day) after the cetuximab loading dose (Day 0).
- 7.2.3 Normal Oral Mucosa Sampling: Baseline EGFR of the normal oral mucosa will be obtained by buccal swab or normal mucosa biopsy. If using buccal swabs, at least 3 normal oral mucosa buccal swab

samples will be acquired. This sampling will occur at both Research Biopsy #1 and Research Biopsy #2.

**7.3 Cetuximab/Radiation Schedule:** Cetuximab will be delivered as standard of care per the package insert.

- 7.3.1 Day 0: Patients will receive a single dose of cetuximab 400 mg/m^2.
- 7.3.2 Day 7 (+/- 1 day): Biopsy #2 will be obtained
- 7.3.3 Following the biopsy, within approximately 4 days, daily radiation therapy with weekly cetuximab will be initiated.
- 7.3.4 Patients will receive weekly cetuximab 250 mg/m^2. On days of radiation therapy and cetuximab administration, cetuximab will be given prior to radiation therapy.

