**7.4 Cetuximab Dose Levels and Modifications**

	Starting Dose	Dose Level –1	Dose Level –2
Cetuximab	400 mg/m  (day 0) 250 mg/m  (day 7 and weekly during RT)	200 mg/m  (weekly)	150 mg/m  (weekly)

NOTE: Once the dosage of cetuximab has been decreased, it will remain at that level unless further dose reductions are required, at which time all dosages will remain at that level. Dosages CANNOT be increased once a dose reduction has taken place.

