## 8.0 Study Calendar

Assessment	Pre-Treatment*	Day 0 Loading Dose	Day 7	Weekly during RT†	1 mo post RT 	12-14 wks post RT 	Follow Up Years 1 and 2 
H&P/Physician Evaluation 	X			X	X	X	X
Research Biopsy	X**		X				
Dental Evaluation 	X						
COMP, Mg	X			X		X	
CBCP with diff	X			X		X	
CT-PET 	X					X	
CT or MRI of head/neck	X						
Toxicity Evaluation	X			X	X	X	X
QOL Questionnaire	X			end of treatment	X	X	X
Cetuximab		X		X			

\* The pre-treatment period is prior to the administration of the cetuximab loading dose. The pre-treatment toxicity evaluation and QOL Questionnaire may be completed at the time of consent. When a patient is determined eligible and enrolled, data will be used. If patient is not eligible or not enrolled, the data will not be used and the subject will be deemed a screen failure. The forms will be kept with the Informed Consent in the study record.

\*\* Research biopsy #1 must be within 4 weeks of loading dose (Day 0)

† Radiation therapy will start within approximately 4 days following Day 7 (+ or – a day) biopsy

Evaluations pre-treatment are by Radiation Oncology, Otolaryngology, and Medical Oncology. Evaluations weekly during RT are generally by Radiation Oncology via standard on-treatment notes. Evaluations in follow up will be by Radiation Oncology, Otolaryngology, and/or Medical Oncology. It is not necessary for patients to be seen by more than one discipline at each follow up visit.

Follow up: Examinations will be performed as comparable to clinical practice: at approximately 1 month following completion of RT and then approximately every 2 months during years 1 and 2. At approximately 12-14 weeks post-RT, patients will have clinical restaging performed for disease evaluation. A PET or MRI is acceptable for this restaging. Toxicity Evaluation and QOL Questionnaires will be collected at each of these visits. Biopsies, labs and imaging studies will be performed as clinically indicated. For years 3 - 5, all follow up will be as clinically indicated and patients will only be followed for disease status and survival.

 Pre-treatment PET-CT and pre-treatment dental evaluation preferred, but these will be ordered at the discretion of the treating physician.

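### Sections 12.4 and 7.4 fix the start of radiation and of the 250 mg/m² infusion at Day 7 while other sections count from Biopsy #2, and the evaluability rule would not screen out a Day 8 biopsy taken after that start

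*Combined protocol and SAP*

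**What the plan says.** The loading dose defines Day 0 (section 7.3.1). For what follows, the protocol uses two kinds of rule.

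- **Fixed day, no window.** Section 12.4, on radiation: "Definitive radiotherapy will begin one week following the administration of the loading dose of cetuximab". The dose table in section 7.4, on the 250 mg/m² infusion: "day 7 and weekly during RT".
- **Counted from Biopsy #2.** Section 7.2.2 sets the biopsy window: "This will be done 7 days (+/- 1 day) after the cetuximab loading dose (Day 0"). Section 7.3.3 then says: "Following the biopsy, within approximately 4 days, daily radiation therapy with weekly cetuximab will be initiated". Section 7.1 has "Within approximately 4 days, definitive radiation will begin", and the calendar footnote in section 8.0 has "Radiation therapy will start within approximately 4 days following Day 7 (+ or – a day) biopsy".

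On order, section 1.1 places the Day 7 biopsy ahead of the concurrent cetuximab and radiation, and section 7.3.3 starts both only once the biopsy has been done.

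In the statistical section, 21.2 makes a patient evaluable for the primary objectives if both research biopsies were taken and treatment was either completed or stopped for toxicity; unevaluable patients are replaced. Section 21.3.1 tests marker change from before to after the loading dose, and 21.3.2 relates that change to clinical outcome. None of these three places any condition on what treatment was given before Biopsy #2.

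**The concern.** Primary Objective 1 is marker change after the loading dose alone. Primary Objective 2, on which section 21.4 bases the sample size, uses the same change as a predictor of progression-free survival. Both need Biopsy #2 to reflect one 400 mg/m² dose and nothing else. A biopsy taken after a second infusion or a 2 Gy fraction measures a different exposure, and mixing the two adds treatment-order variation to the marker data.

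The operative text gives sites two start rules. Sections 16 and 19 provide for several participating sites, and a radiation team working from section 12, an infusion team working from the 7.4 table and a coordinator working from the calendar could each schedule differently. If that led to a misordered biopsy, nothing in section 21 would identify or exclude it.

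**Working it through.** The plan has no figure of its own to reproduce here: the power inputs in section 21.4 involve neither biopsy timing nor radiation timing. The check is a count of study days.

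**Inputs.** Biopsy day b = 6, 7 or 8 (7.2.2). Start day under the biopsy-anchored rule = b + k, with k = 0 to 4 whole days (7.1, 7.3.3, 8.0). Start day under the fixed rule = 7 (12.4 for radiation, 7.4 for the 250 mg/m² infusion).

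| Biopsy day | Biopsy-anchored start, b to b + 4 | Fixed Day 7 start relative to the biopsy (7 − b) |
|---|---|---|
| 6 | Day 6 to 10 | +1: one day after the biopsy |
| 7 | Day 7 to 11 | 0: same day |
| 8 | Day 8 to 12 | −1: one day before the biopsy |

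**Range.** The biopsy-anchored start runs from Day 6 to 8 + 4 = Day 12. The upper end is soft, because the text says approximately 4 days. Against the fixed Day 7 the gap is up to about 12 − 7 = 5 days.

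**Where the rules agree.** Of the 3 × 5 = 15 biopsy and start combinations, two give a Day 7 start: b = 6 with k = 1, and b = 7 with k = 0. In the second, the biopsy must also come first within the day. These two satisfy all the cited passages.

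**Where they do not.** One combination starts on Day 6 (b = 6, k = 0). The other 3 + 4 + 5 = 12 start on Day 8 or later. For a Day 8 biopsy no value of k from 0 to 4 gives Day 7, so the fixed and anchored rules cannot both be met.

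**Order.** Under the biopsy-anchored rule, none of the 15 combinations starts treatment on a day before the biopsy. Under the fixed rule, only b = 8 does, by one day.

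**Safeguard.** Take a patient with a Day 8 biopsy whose radiation or second infusion began on Day 7. Both biopsies were taken, so once treatment is completed or stopped for toxicity, 21.2 counts the patient as evaluable, and 21.3.1 and 21.3.2 use the change as a loading-dose change.

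**Calendar.** The cetuximab row is marked at Day 0 and weekly during radiation, with nothing under Day 7. I give this little weight, since an infusion on the first day of radiation could belong in the weekly column.

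**The case against.** The strongest reply is that the protocol already settles the order. Section 7.3.3 is the operative schedule and makes the biopsy the trigger for both radiation and weekly cetuximab; 7.1 and the calendar footnote also count the radiation start from the biopsy; 1.1 states the same sequence. No passage tells a site to take Biopsy #2 after further treatment. Section 12.4 can be read as a round-number summary and the day in the 7.4 table as a nominal target. On that view this is an editorial mismatch.

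Much of this stands. A reader might infer that the start rules can never be met together; the documents do not support that, because a Day 6 or Day 7 biopsy with a Day 7 start meets them all. A reader might also infer that the protocol as a whole permits Biopsy #2 after treatment has resumed; 1.1 and 7.3.3 say otherwise, so reaching that state means applying 12.4 or 7.4 in isolation.

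What the reply does not remove is that 12.4 and 7.4 are themselves operative instructions, written without a window, and that a Day 8 biopsy is expressly allowed. Nor does it supply a check in section 21: the intended order appears in the treatment text but is not a condition for a sample to enter the marker analysis.

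**Conclusion.** The passages on the start of radiation and of the 250 mg/m² infusion are inconsistent for a Day 8 biopsy or any start after Day 7, and must be reconciled. A misordered Biopsy #2 is a risk created by that inconsistency, not something the protocol intends, and section 21.2 would let such a sample through.

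The number of patients affected cannot be derived from the documents. It is zero if every site follows 7.3.3; otherwise it depends on how often Day 8 is used and which section a site schedules from, and neither is given. It is tempting to divide 50 patients evenly over three days and call about 17 exposed. That needs an even spread, although Day 7 is the target and the other days are tolerance, and it needs every Day 8 patient to be treated on Day 7 contrary to 7.3.3. The documents support neither assumption.

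The point is not fatal to the design, but it should be corrected, because it bears on the measurement behind two primary objectives. I take no view on which start day is right.

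**What to change.** 1. Reconcile sections 7.1, 7.3, 7.4, 8.0 and 12.4 to one timetable chosen by the sponsor, consistent with the biopsy-first order already in 1.1 and 7.3.3.
2. In 21.2 and 21.3.1, state that Biopsy #2 is the post-loading-dose sample only if it was taken before the second cetuximab infusion and before the first radiation fraction. Because 21.2 defines evaluability for all primary objectives together, limit this condition to the marker objectives, so that a patient with a misordered biopsy is not also lost from the toxicity description.
3. Record the date and time of Biopsy #2, of the second infusion and of the first fraction. Dates alone cannot settle the order when the biopsy and the start fall on the same day.
4. Report any other Biopsy #2 samples separately, with their number.

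The cost is amendment wording and a few time fields on the case report form. The downside is that a few patients may be unevaluable for the marker objectives and need replacing, which 21.2 already provides for.

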### 12.5 Radiation Fields:

The treatment volumes will be individualized for each patient depending upon the extent of disease. Tumor volumes will be outlined on the planning CT scans with the aid of CT-PET to ensure adequate irradiation of the pre-cetuximab tumor volume. Treatment techniques will aim at adequate irradiation of the clinical and the sub-clinical disease. The therapy goals, specifying the intended doses to the primary tumor and lymph node metastases, will be detailed in the therapy chart. A CT-based display of the isodoses will be recorded, such that it will be feasible to assess whether the intended (prescribed) isodoses cover the targets adequately.

### 12.6 Doses:

Tumor doses will be expressed in Gy. The prescribed doses should encompass the targets. Treatment plans will be generated demonstrating adequate coverage of the target volume. The dose across the target volume should not vary by more than +/- 10% of the prescribed dose. When an anterior-posterior low neck field is treated, the dose will be prescribed to 3cm depth. For electron beam treatments, the dose will be prescribed to the depth at which maximum dose is obtained (Dmax). When treating the posterior cervical nodes, either six or nine MeV electrons may be used. Treatment will be delivered daily, five days per week, 2.0 Gy per fraction. Total dose to gross disease will be 70 Gy and subclinical disease dose will be 50-60 Gy. Intensity Modulated Radiation Therapy (IMRT) will be used to decrease dose to the normal critical structures when appropriate, as determined by the treating radiation oncologist.

### 12.7 Immobilization and Positioning:

All patients will be treated in a position that affords maximal daily reproducibility. Commonly, it will be in the supine position. Immobilization devices such as head masks or bite blocks are mandatory to ensure that target volumes are adequately treated. Cradles or arm restraints may be needed to allow adequate exposure of the lower neck area in selected patients.

### 12.8 Simulation and CT Scanning:

All patients will undergo simulation including a CT scan. Treatment planning CT scans with or without contrast will be obtained on each patient prior to the first week of cetuximab to ensure adequate radiation of the pre-cetuximab tumor extent.

### 12.9 Technical Factors:

Equipment - Megavoltage equipment with a source to skin distance of 100cm (or source-axis distance), or greater, will be used. Megavoltage machines with an energy equal to 6 MV photons will be used, rarely higher energy may be used if necessary.

### 12.10 Treatment Planning:

CT based planning may be used for the total course of radiation, especially if necessary for parotid sparing purposes. Otherwise, the final boost may be planned or the full course of radiation may be planned using orthogonal simulation fields alone,

using the information from the pre-cetuximab planning CT for verification of the adequacy of the radiation fields.

#### 12.11

##### Treatment Interruptions:

It is expected that the entire treatment for definitive irradiation will be completed in about 7-8 weeks. Treatment interruptions due to symptomatic mucositis or skin reactions are rare. In the case of severe mucositis, preventing appropriate nutritional intake, a gastric tube or dohoff tube will be inserted and radiation will continue uninterrupted at the discretion of the treating physician. Weight will be recorded weekly in the Radiation Oncology chart. If the patient's weight loss exceeds 10% of the initial weight or if the patient is malnourished before radiation, a feeding tube may be inserted by an appropriately trained physician (surgeon, gastroenterologist, interventional radiologist) as defined by clinical practice.

#### 13.0 EGFR analysis (General Laboratory Guidelines)

The primary goal of this analysis is to determine whether cetuximab given at the clinically recommended dose, will inhibit EGFR phosphorylation and down-stream signaling effects within the tumor as well as the normal mucosa following therapy. In addition, the activation of EGFR and various down-stream signaling markers will be measured using immunoblotting as well as immunohistochemical analysis in both normal and tumor samples at baseline and post-treatment.

#### 13.4

##### Pre-Cetuximab tumor

The initial pre-treatment punch-biopsy specimen (about 3x3x3 mm) of the tumor will be collected in the presence of a laboratory personnel and will be immediately frozen in dry-ice ethanol bath in Tissue-Tek O.C.T Compound (Sakura Finetek, Torrance, CA) to ensure the integrity of tissue and phosphoproteins for both immunoblotting and immunohistological analysis of samples. We will be able to take 3 cores for TMA construction from a single 3x3x3 mm biopsy and will expect to have enough material to get about 30-50 4-5 micrometers thick sections for immunohistochemical analysis.

